2.3. Timing of analysis

An initial analysis will be carried out after six months follow-up has been achieved for all patients, therefore including data up until 1st January 2021. A further analysis will include data up to one year, i.e. 1st July 2021.

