11.2. Description of the Statistical Methods

Primary outcome

The primary outcome will be all-cause mortality at 1 year after discharge from ICU. For patients transferred between ICUs, this will be the time of discharge from the last ICU. Dates of death will be extracted from Civil Registration (deaths).

Secondary outcomes

Secondary outcomes will be:

- All-cause mortality at 30, 60, 90 and 180 days
- Any emergency (non-elective) hospital admission
- Emergency hospital admissions for respiratory infection
- Emergency hospital admission for a venous thrombotic event (deep vein thrombosis or pulmonary embolism)
- Emergency hospital admission for a major adverse cardiac event (myocardial infarction, stroke, heart failure)
- Development of end stage renal failure treated by renal replacement therapy

Reasons for hospital admission (i.e. primary diagnosis) will be identified using the International Classification of Diseases 10th Edition (ICD- 10) codes obtained by linkage to the HES/PEDW. Where required, ICD-10 codes will be assigned to broader diagnostic groups (e.g. respiratory infections) as per the UK Summary Hospital-level Mortality Indicator (SHMI) (16).

Statistical methods

For patients treated on ICU for COVID-19 and comparator groups, we will report the unadjusted proportions/incidence of primary and secondary outcomes, along with cumulative incidence function estimates over the 1 year follow-up period. When considering secondary outcomes (and where appropriate), the cumulative incidence estimates will account for the competing risk of death. For the COVID-19 group, we will also investigate the effect of ICU admission time (i.e. early epidemic, late epidemic) as this may impact their outcomes, as treatments changed over time.

We will compare the risk of the primary and secondary outcomes between the COVID-19 and comparator groups using survival models, such as Cox proportional hazards regression models or Fine and Gray models (when death is a competing risk). We will fit both univariable models (i.e. just including the COVID-19 vs comparator group variable) and multivariable models including potential confounders.

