2.4. Timing of outcome assessments

The primary outcome will be at 1 year after discharge from ICU. Secondary outcome assessments will be made at 30, 60, 90 and 180 days after discharge.

3. Statistical principles

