4.4. Cohort definitions

4.4.1. Patients with confirmed COVID-19 between 1st January to 1st July 2020 This group will consist of all individuals who were admitted to an intensive care unit between 1st January and 1st July 2020 with a confirmed diagnosis of COVID-19.

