4.4.4. Non-COVID ICU admissions 1st January 2020 – 1st July 2020

All emergency ICU admissions between 1st January 2020 and 1st July 2020 where the primary diagnosis was not COVID-19. This cohort includes patients admitted to ICU concurrently to the primary COVID-19 cohort. While this cohort will likely be small, it will possibly provide a fairer comparison of outcomes if the pandemic did affect the healthcare provision during follow-up (i.e. if there were a reduction in the number of hospital admissions for non-Covid causes during the period of the pandemic due to restrictions).

5. Analysis

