5.4. Analysis methods

5.4.1. Descriptive analysis of incidence

The incidence of each of the primary and secondary outcomes will be summarised within each cohort. Kaplan-Meier curves will be used to graphically display the number of patients who die in the follow-up period, whilst cumulative incidence function curves will be used to display all of the secondary outcomes (treating death as a competing risk). The number and proportion of patients experiencing each event will be tabulated at each of the outcome assessment time points. Further analyses will investigate the event rates within relevant subgroups (described in Section 5.5). For continuous variables (such as age) we will additionally consider regression modelling with non-linear terms (e.g. fractional polynomials or restricted cubic splines) to describe the impact of the variable on the patient's risk of experiencing the outcome events.

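### The data cuts in SAP 2.3 count from the last ICU admission but outcomes count from ICU discharge, so the latest 2020 patients fall short of 180 and 365 days

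*SAP*

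**What the plan says.** Eligibility closes on an admission date. SAP 4.4.1 takes COVID-19 patients "admitted to an intensive care unit between 1st January and 1st July 2020 with a confirmed diagnosis of COVID-19", and SAP 4.4.4 defines the concurrent comparator as "All emergency ICU admissions between 1st January 2020 and 1st July 2020 where the primary diagnosis was not COVID-19".

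The outcome clock starts later. SAP 2.4 states: "The primary outcome will be at 1 year after discharge from ICU". It adds: "Secondary outcome assessments will be made at 30, 60, 90 and 180 days after discharge". For patients moved between units, Protocol 11.2 says of the starting point that "this will be the time of discharge from the last ICU".

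SAP 2.3 nevertheless fixes calendar dates. The first analysis comes "after six months follow-up has been achieved for all patients, therefore including data up until 1st January 2021". For the second: "A further analysis will include data up to one year, i.e. 1st July 2021".

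Other sections point to longer follow-up. Protocol 7.3 and 12.1 request one year of data per patient after hospital discharge. Protocol 8.3 and 11.5 and SAP 4.1.2 place the linkage for 365-day outcomes in October 2021. For 180-day outcomes the protocol names March 2021 and SAP 4.1.2 names July 2021.

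On reporting, SAP 5.4.1 plans Kaplan-Meier curves for death and cumulative incidence curves for the secondary outcomes, and then: "The number and proportion of patients experiencing each event will be tabulated at each of the outcome assessment time points".

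**The concern.** The cut dates work only if follow-up starts at ICU admission, and no section says that it does. For the latest patients the plan therefore claims follow-up that it will not have, at the primary time point as well as at 180 days.

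The shortfall is uneven between groups. It affects patients still in ICU at the start of July 2020, all of whom belong to the COVID-19 cohort or the concurrent 2020 cohort, apart from extreme stays in earlier cohorts. The primary comparator in Protocol 11.4, pneumonia admissions to 1 July 2019, has ample time. Among late admissions, those with the longest ICU stays lose the most days.

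Neither document gives a censoring date or a denominator rule for the tabulated proportions. If all patients stay in the denominator, unobserved days count as event-free and the crude proportion is too low. If short follow-up were instead handled as missing data, the complete-case rule in SAP 5.7 could remove late, long-stay patients.

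**Working it through.** **Inputs.** Last eligible admission 1 July 2020 (SAP 4.1.1, 4.4.1, 4.4.4). Cuts 1 January and 1 July 2021 (SAP 2.3). Clock from last ICU discharge (SAP 2.4, Protocol 11.2). COVID-19 survivors 4,600 (SAP 2.2). Let L be the days from ICU admission to last ICU discharge; the documents give no values for L.

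**Reproducing the plan's dates.** From 1 July 2020 to 1 January 2021 is 184 days, and to 1 July 2021 is 365 days. The dates are reproduced exactly if the clock starts at admission.

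**Counting from ICU discharge.** A last-day admission has 184 − L days at the first cut and 365 − L at the second.

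| L (days) | To 1 Jan 2021 | To 1 Jul 2021 |
|---|---|---|
| 5 | 179 | 360 |
| 14 | 170 | 351 |
| 30 | 154 | 335 |
| 60 | 124 | 305 |

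Working back from the cuts, 365 days requires ICU discharge by 1 July 2020. A 180-day window requires discharge by 5 July 2020, so the first cut has 184 − 180 = 4 days of slack.

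**Earlier cohorts at the final cut.** For admissions ending 1 January 2020 there are 547 days, so 365 is missed only if L exceeds 547 − 365 = 182. For admissions ending 1 July 2019 there are 731 days, so L would have to exceed 731 − 365 = 366.

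**Share affected (assumption).** With even admissions over the 182-day window, the share still in ICU on 1 July 2020 is mean L / 182. Mean L of 5 gives 5/182 = 2.7% (about 126 of 4,600); mean L of 30 gives 30/182 = 16.5% (about 758). If late-June admissions ran at 10% to 50% of the average rate, the range is about 13 to 379.

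**Effect on a crude one-year proportion (assumption).** Take a true risk of 10% and a constant daily hazard h = −ln(0.9)/365 = 0.000289. If a share s is short by k days, the crude proportion is (1 − s) × 0.10 + s × [1 − exp(−h(365 − k))].
- s = 3%, k = 5: 9.996%.
- s = 16%, k = 15: 0.84 × 0.10 + 0.16 × 0.09609 = 9.94%, a loss of 0.06 percentage points.
- The same s and k with a 20% risk: 19.88%, a loss of 0.12 points.
- s = 16% and 10% risk, but k = 30: 0.84 × 0.10 + 0.16 × 0.09217 = 9.87%, a loss of 0.13 points.

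**What the linkages could supply.** Taking the three-month delay in SAP 4.1.2 at face value, an October 2021 linkage has complete HES and audit data to between 1 and 31 July 2021. That covers 365 days for a last-day admission with L up to 0 to 30 days. The SAP's July 2021 linkage would reach at least 1 April 2021, which is 274 days, and so covers 180 days for L up to 94.

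**The case against.** The strongest reply is that little of the analysis depends on these dates. SAP 5.4.1 already plans Kaplan-Meier and cumulative incidence curves, and SAP 5.4.2 and 5.4.3 compare cohorts by Cox and competing-risk models. All of these accommodate administrative censoring. This stands, and it confines the problem to the table of numbers and proportions and to the wording of SAP 2.3.

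A reader might infer that the three-month delay leaves the primary outcome incomplete after July 2021. The documents do not say so: the delay is described as possible and is stated for HES and national audit data, whereas deaths come from Civil Registration, for which no delay is given. A reader might also infer that the design cannot deliver a full year. In fact the October 2021 linkage and the per-patient request for a year after hospital discharge could supply much or all of the missing time; the fixed cut in SAP 2.3 discards it. Nor are long stays at risk in general: a 60-day stay that began in March or April 2020 ends before 1 July and loses nothing.

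It is also fair that the claim about all patients is attached only to the six-month analysis, where four days of slack exist against 180 days. Even so, it fails for any last-day admission with L above 4, and SAP 2.3 equates one year with 1 July 2021 without qualification.

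**Conclusion.** The inconsistency is certain, since it follows from the plan's own dates: SAP 2.3 counts from admission and SAP 2.4 from ICU discharge. The statement that six months is achieved for all patients is wrong, and some patients will lack 365 days at the final cut if any remained in ICU after 1 July 2020.

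The numerical consequence is probably small. On a 10% one-year risk with constant hazard, and 3% to 16% of patients short by 5 to 15 days, a crude proportion is low by about 0.06 percentage points or less. Higher risks or longer shortfalls scale this up, to 0.12 or 0.13 points in the variants shown. A hazard that falls over the year would make it smaller. Stay lengths and the calendar pattern of admissions are not in the documents, so these are illustrative ranges, and the downward direction assumes that all patients stay in the denominator.

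The documents do not support a conclusion that the primary hazard ratio is materially biased, or that the one-year comparison is invalid.

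**What to change.** In SAP 2.3, replace the fixed dates with a per-patient window of last ICU discharge plus 180 days and plus 365 days, drawing on the October 2021 linkage and the data request already planned. Reconcile that section with SAP 2.4 and 4.1.2 and with Protocol 8.3, 11.5 and 12.1, including the differing dates for the first linkage.

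State a data-completeness date, set separately for deaths and for HES and audit data, and censor at that date any patient not followed to the end of the window. In SAP 5.4.1, take the 180-day and one-year proportions from the planned Kaplan-Meier and cumulative incidence estimates instead of dividing events by all patients, and show numbers at risk.

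The cost is minor SAP rewording. If the linkage date is kept, a few late patients remain censored, which the estimators allow for. The extract need not wait for the very last discharge; that would let one very long stay set the timetable, and a later linkage could require a protocol amendment.

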2.4. Timing of outcome assessments

The primary outcome will be at 1 year after discharge from ICU. Secondary outcome assessments will be made at 30, 60, 90 and 180 days after discharge.

3. Statistical principles

3.1. Multiplicity

We do not plan to make any adjustments to p-values or confidence intervals. To reduce the impact of multiple testing, we will only report p-values for the primary outcome measure (i.e. death). All analyses of secondary outcomes will only present the effect size and the 95% confidence interval.

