We will also analyse the data using propensity score matching as an alternative method to account for any potential confounding associated with the COVID-19 and comparator populations. A logistic propensity score will be used to create a matched population. The following variables will be considered for inclusion in the propensity score:

- Age at discharge from hospital
- Charlson/Elixhauser comorbidity index
- Ethnicity
- Illness severity (APACHE-II or ICNARC severity score) on admission to ICU
- Days of mechanical ventilation
- Week of the year of ICU admission (to account for potential increased survival over the course of the pandemic)

As an exploratory analysis, we will examine potential prognostic factors (such as patient or ICU treatment characteristics) for the primary and secondary outcomes. We will further investigate whether some of the secondary outcomes are time-varying predictors of mortality. Latent class analysis may also be used to identify any clustering of the secondary outcomes and their severity and/or timing.

Where common patient data items are available from multiple data sources (e.g. age, gender ethnicity), we will develop a standard protocol to resolve inconsistencies. Should substantial differences remain, we will explore any effect on our results through a sensitivity analysis.

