3.2. Statistical significance and confidence interval

We will consider a p-value < 0.05 as statistically significant, and therefore we will present 95% confidence intervals.

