5.3. Outcome definitions

5.3.1. Primary outcome

Death – death from any cause, as recorded in the civil registrations data set. As per Section 2.4 the primary analysis will be at one-year post-discharge. Comparisons at 30, 60, 90 and 180 days will be secondary analyses of the primary outcome.

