5.4.2. Comparison of COVID-19 cohort to other cohorts using standard regression modelling

To compare the risk of the primary outcome (death) between the COVID-19 cohort and the other cohorts, we will use Cox proportional hazards regression models to estimate the hazard ratio (and 95% confidence interval). The hazard ratio (HR) will be calculated at each of the outcome assessment time points. For the secondary outcomes, a competing risk approaches will be used, with death as the competing risk. We will use the cause-specific Cox proportional hazards regression approach to estimate the cause-specific hazard ratio (and associated 95% confidence interval). The Fine-and-Gray approach will be used as a sensitivity analysis to estimate the sub-distribution hazard ratio. For each of these analyses we will report unadjusted results.

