5.6. Sensitivity analyses

To assess the robustness of the propensity-matched analysis, we will also fit multivariable regression models. We will use restricted cubic splines or fractional polynomials to allow for potentially nonlinear relationships between continuous covariates and outcomes. The adjustment variables will be those listed in Section 5.2.

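### SAP 3.1 limits p-values to death but fixes no single primary comparator-and-method test, leaving 9 death p-values at 1 year and up to 45 in all, each judged at 0.05

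*SAP*

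**What the plan says.** On error control, SAP 3.1 states "We do not plan to make any adjustments to p-values or confidence intervals" and gives its only safeguard as "To reduce the impact of multiple testing, we will only report p-values for the primary outcome measure (i.e. death". SAP 3.2 adds: "We will consider a p-value < 0.05 as statistically significant, and therefore we will present 95% confidence intervals".

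On what is tested for death:

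- **Time.** SAP 2.4 and 5.3.1 make 1 year primary. SAP 5.3.1 continues: "Comparisons at 30, 60, 90 and 180 days will be secondary analyses of the primary outcome". Protocol 11.2 puts "All-cause mortality at 30, 60, 90 and 180 days" in its list of secondary outcomes. SAP 5.4.2 says: "The hazard ratio (HR) will be calculated at each of the outcome assessment time points".
- **Comparator.** SAP 4.4.2 to 4.4.4 define three cohorts: emergency admissions July 2016 to July 2019, the same extended to January 2020, and concurrent non-COVID admissions in the first half of 2020. Protocol 11.4 names a different primary comparator, pneumonia admissions from July 2016 to July 2019.
- **Method.** Unadjusted Cox (SAP 5.4.2), propensity-matched Cox (SAP 5.4.3) and multivariable Cox (SAP 5.6). On their order, Protocol 11.2 sets out the Cox and Fine-Gray models and then says "We will also analyse the data using propensity score matching as an alternative method to account for any potential confounding". SAP 5.6 says "To assess the robustness of the propensity-matched analysis, we will also fit multivariable regression models".

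**The concern.** Restricting p-values to one outcome limits chance findings only if that outcome is tested once, or a few times in a stated order. Here death is compared against several cohorts by several methods, with no p-value designated as the answer to the primary objective. The one comparator that the protocol calls primary has no cohort definition in the SAP, and the two documents order the methods differently.

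The status of early mortality decides how far the SAP 3.1 rule reaches, and the documents disagree on it. As secondary outcomes (Protocol 11.2), the 30 to 180 day comparisons would get no p-value. As analyses of the primary outcome (SAP 5.3.1), they may.

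At stake is whether a mortality difference called significant could be one of several unranked results, with a chance error rate well above the 5% that a reader would assume.

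**Working it through.** **The plan's own figures.** The only stated error rate is 0.05 per test; the 95% intervals imply that it is two-sided. One test gives 1 − 0.95^1 = 5%. The sample size also reproduces: 90,000 × 3.5 + 4,600 = 319,600. The documents state no familywise rate and no number of tests.

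**Count.**

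- 1 year only: 3 cohorts × 3 methods = 9.
- All five time points: 3 × 3 × 5 = 45.
- Adding the protocol's pneumonia cohort without ranking the tests: 4 × 3 = 12 and 4 × 3 × 5 = 60.

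Subgroups and the exploratory comparisons in SAP 1.2 are left out.

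**Ceiling if the tests were independent.** 1 − 0.95^9 = 37.0%; 1 − 0.95^45 = 90.1%. These tests are far from independent, so this is an upper bound only.

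**Allowing for overlap.** Null z statistics were simulated (100,000 replicates, threshold |z| > 1.96) with this structure:

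- The same 4,600 COVID-19 patients enter every test. Cohort 4.4.2 has 3 × 90,000 = 270,000 patients and lies inside cohort 4.4.3, which has 315,000.
- Time windows are nested, so the correlation between two windows is √(f_i/f_j), where f is the share of one-year deaths reached.
- Unadjusted tests against 4.4.2 and 4.4.3 are almost the same test: √[(1 + 4,600/315,000)/(1 + 4,600/270,000)] ≈ 0.999.
- 1:1 matched control sets for 4.4.2 and 4.4.3 overlap by 270/315 = 6/7, giving correlation (1 + 6/7)/2 ≈ 0.93. Matched tests against 4.4.2 and 4.4.4 share only the COVID-19 arm, giving 0.5.
- Unadjusted and matched tests against 4.4.2 correlate at 1/√[2 × (1 + 4,600/270,000)] ≈ 0.70.

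Assumptions that the documents do not supply:

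- Deaths by 30, 60, 90 and 180 days as a share of one-year deaths: 40/52/60/78%, 25/37/46/68%, or uniform (8/16/25/49%).
- Correlation between unadjusted and multivariable z: 0.80, 0.90 or 0.98.
- Size of cohort 4.4.4: 45,000, with one run at 20,000 (uniform accrual, correlation 0.80).

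Chance of at least one p < 0.05 with no true difference:

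| Tests | Number | If independent | With overlap |
|---|---|---|---|
| One named test | 1 | 5.0% | 5% |
| Matched, 1 year, three cohorts | 3 | 14.3% | about 10.5% |
| Matched, one cohort, five time points | 5 | 22.6% | 12% to 17% |
| All methods and cohorts, 1 year | 9 | 37.0% | 15% to 17% |
| Matched, all cohorts and time points | 15 | 53.7% | 24% to 32% |
| All methods, cohorts and time points | 45 | 90.1% | 32% to 48% |

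The expected number of false positives among the 45 is 45 × 0.05 = 2.25 (simulated 2.23 to 2.27). They arrive in clusters, which is why the chance of any is well below 90%.

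The runs take every test, including the unadjusted ones, to be null. They describe chance only. A case-mix difference in the unadjusted comparison is a separate source of small p-values. The matched-only rows do not depend on the unadjusted tests.

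**The case against.** The SAP ranks more than it may seem to. One year is primary. Cohort 4.4.3 is introduced as a robustness check on 4.4.2, and SAP 5.6 makes the multivariable model a sensitivity analysis. Taken at face value, this leaves two cohorts (4.4.2, 4.4.4) and two methods (unadjusted, matched) unranked at 1 year: 2 × 2 = 4 contenders. SAP 6 presents the different cohorts and methods as checks on robustness, not as separate routes to a claim, and many cohort studies leave such checks unadjusted.

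SAP 3.1 also promises to reduce multiple testing, not to control it, and it does reduce it. Withholding p-values from five secondary outcomes at two time points, over three cohorts and three methods, removes 5 × 2 × 3 × 3 = 90 tests. The SAP is open about making no adjustment.

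All of this stands. It answers some stronger readings that a reader might infer:

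- *That nothing is primary.* The time point is named in the SAP and a comparator is named in the protocol. What is missing is one comparator and method together.
- *That 45 is a minimum.* It is an upper count of the overall comparisons and depends on SAP 5.3.1. SAP 2.4 and Protocol 11.2 support 9, and SAP 5.4.2 promises hazard ratios with intervals, not a printed p-value at each time.
- *That subgroups add many more p-values.* SAP 5.5 says only that subgroups will be investigated. It gives no levels and no tests.
- *That Protocol 11.2 declares regression the main method.* It puts regression first and calls matching an alternative, but labels nothing as main.

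The objection does not supply a primary test. Even with the SAP's own rankings, the choice between cohorts 4.4.2 and 4.4.4, and between unadjusted and matched results, stays open, and neither cohort is the protocol's primary comparator.

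**Conclusion.** The concern holds in a limited form. SAP 3.1 narrows testing to death but leaves 9 p-values at 1 year, and up to 45 over all time points, each at 0.05, with no single comparator-and-method test fixed as primary. With no true difference, the chance of at least one p < 0.05 is about 15% to 17% for the 9, roughly three times nominal, and about 32% to 48% for the 45. These ranges rest on the assumed death accrual, between-model correlation and size of the concurrent cohort.

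A reader might infer that a false positive is more likely than not. The documents do not support that. The 90% figure requires independent tests, and every modelled range for the overall comparisons stays below one half.

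The conflicts between the documents need no assumption: SAP 4.4 lacks the Protocol 11.4 primary comparator, the role of matching differs, and so does the status of 30 to 180 day mortality.

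**What to change.** 1. Add the pneumonia cohort (July 2016 to July 2019) to SAP 4.4, or reconcile SAP 4.4 with Protocol 11.4.
2. In SAP 3.1, name one primary test: all-cause death at 1 year, COVID-19 against that comparator, by the propensity-score Cox analysis chosen under SAP 5.4.3. Because that section allows nearest-neighbour matching, full matching or weighting, state that the choice is made on covariate balance before outcomes are examined.
3. Print a p-value for that test only. Give every other death analysis (30 to 180 days, other cohorts, unadjusted, multivariable, subgroups, the six-month analysis) as estimate and 95% CI without significance wording. This is the SAP's own rule for secondary outcomes, and it removes the need to settle the status of early mortality for p-values.
4. Align the order of methods in Protocol 11.2 and SAP 5.6.

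The single designated test is then at 5%. The cost is fewer printed p-values and one extra cohort definition, with its matching run. No estimate is lost.
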